6 STUDY ENDPOINTS

6.1 EFFECTIVENESS ENDPOINTS

The following endpoints will be assessed:

- **Primary effectiveness endpoint**
 - Mean Change from baseline in Tear Break-Up Time (TBUT)
- **Secondary effectiveness endpoints**
 - Mean Change from baseline in OSDI score²²
 - Mean Change from baseline in the total Meibomian Gland Secretion Score²³

²² Schiffman RM, Christianson MD, Jacobsen G, Hirsch JD, Reis BL. Reliability and validity of the Ocular Surface Disease Index. Arch Ophthalmol 2000;118: 615-621.

²³ Bron AJ, Benjamin L, Snibson GR. Meibomian gland disease. Classification and grading of lid changes. Eye 1991;5: 395-411.

- Mean Change from baseline in corneal staining scores
- Mean Change from baseline in conjunctival staining scores

6.2 SAFETY ENDPOINTS

Safety will be assessed by evaluating the following measures over time:

- Device-related adverse events (all adverse events will be recorded)
- Best spectacle-corrected visual acuity (Snellen)

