2 STUDY OBJECTIVE

The objective of this study is to evaluate the safety and effectiveness of a single TearCare® procedure to treat adult patients with dry eye disease.

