9.5.3 TEARCARE PROCEDURE

The TearCare procedure should be performed by a clinician who did not perform the Baseline endpoint assessments. Refer to the TearCare Instructions for Use for detailed instructions for operating the TearCare System.

1. Obtain a new set of iLid devices and a TearCare SmartHub with enough battery left for at least one procedure.
2. Wipe the subject's eyelids and temple with the makeup removal wipe provided by the Sponsor. Allow the skin to dry or pad dry with a tissue. Use care not to allow any of the wipe to get into the eye.
3. Place a pair of iLid devices on the subject's eyelids and affix the temple housing to the subject's temple. Use the clip to secure the cables behind the subject's head.
4. Connect the iLid devices to the SmartHub.
5. Inform the subject that the iLid devices will heat up very quickly once the TearCare procedure is started.

6. Start TearCare procedure. Subjects should be encouraged to keep their eyes open and blink naturally during the TearCare procedure.
7. If the subject indicates the temperature is too hot, decrease the temperature set point to a setting that is comfortable for the subject.
8. Following the thermal portion of the TearCare treatment, remove the iLid devices from the subject and position the subject at the slit lamp to perform expression of the meibomian glands. Begin performing expression within 3 minutes of completion of the thermal portion of the procedure.
9. Apply 1 drop of proparacaine or tetracaine into each eye. Apply Akten® (lidocaine hydrochloride ophthalmic gel) 3.5% or equivalent into the lower eyelid fornices.
10. Using the Express Forceps, express the meibomian glands in all 4 eyelids using the following technique:
 - a. Think of each eyelid as having 3 zones: nasal, central & temporal.
 - b. For each zone, start at the fornix and work your way up to the margin.
 - c. Position the forceps horizontal, parallel to the margin.
 - d. Apply moderate continuous pressure and adjust based on the gland output.
 - e. Perform a second pass on the same eyelid to further express the glands.
 - f. After treating the lower and upper eyelids, repeat expression on all 4 lids to ensure complete expression.
 - g. Should the subject experience discomfort, it is reasonable to apply additional topical anesthetic.
 - h. The goal is to express each zone until the meibum coming out is clear.

Typically, complete expression takes approximately 5 minutes/eye.

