10.2 LIST OF ANTICIPATED POTENTIAL ADVERSE EVENTS

Anticipated potential adverse events include those that might reasonably be expected to occur in this study because they are associated with dry eye disease, the risk analysis for TearCare System (albeit remote likelihood), study testing methods or potential risks associated with warm compresses and lid massage.

- Burn, erythema, or swelling of the eyelids
- Conjunctival injection (Moderate or severe)
- Conjunctival abrasion
- Corneal abrasion
- Corneal deformation
- Allergic or inflammatory reaction to medical adhesive on the iLid device
- Formation of a chalazion or stye
- Loss in BSCVA of 2 lines or greater from baseline BSCVA
- Increased discomfort or pain of ocular surface (grittiness, foreign body sensation, etc.)
- Discomfort or pain of eyelids or orbit: Transient discomfort or pain during the TearCare procedure is not considered an adverse event. Persistent pain or discomfort may represent an adverse event, if judged so by the investigator.

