10.3 REPORTING ADVERSE EVENTS AND UNANTICIPATED ADVERSE DEVICE EFFECTS

Identification, collection and reporting of adverse event information is the responsibility of the principal investigator. The investigator records the date of the event, its severity, treatment (if any) and the assessed relationship of the event to the study device on the Adverse Event Case Report Form (AE CRF).

Any ocular-related **serious adverse event** (SAE) should be reported to the study sponsor within one working day of learning of the event. Non-ocular-related SAEs should be

reported to the study sponsor within two working days of learning of the event. Email the AE CRF to [REDACTED].

Any **unanticipated adverse device effects (UADE)** must be reported to the following two entities:

1. The study sponsor – Within one working day of the investigator first learning of the event, e-mail the AE CRF to [REDACTED]; and
2. The reviewing IRB – As soon as possible, but no later than 10 working days after the investigator first learns of the event, report per the IRB's instructions.

The sponsor will conduct an evaluation of unanticipated adverse device effects. If the sponsor determines that an unanticipated adverse device effect presents an unreasonable risk to subjects, parts of the investigation presenting risks will be terminated. Termination will occur no later than 5 working days after the sponsor makes such a determination and no later than 15 working days after the sponsor first received notice of the effect.

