11.4 RISKS ASSOCIATED WITH PARTICIPATION IN THE CLINICAL INVESTIGATION

All anticipated study risks are listed in Section 10.2.

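### The objective is the safety of the TearCare procedure, but the adverse-event endpoint and its attribution cover only the device, so a reaction to the procedural anaesthetics may fall outside the headline safety result

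*Combined protocol and SAP*

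**What the plan says.** Section 2 states the aim as to "evaluate the safety and effectiveness of a single TearCare® procedure", and the synopsis says the same. Section 9.5.3 sets out that procedure as numbered steps. Step 9, between removal of the iLid devices and forceps expression, begins "Apply 1 drop of proparacaine or tetracaine into each eye" and continues with lidocaine gel or an equivalent in the lower fornices. Step 10g allows more topical anaesthetic if the subject is uncomfortable.

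Section 6.2 has two safety measures: "Device-related adverse events (all adverse events will be recorded") and "Best spectacle-corrected visual acuity (Snellen"). The synopsis lists the first without the parenthetical remark.

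On attribution, Section 10.3 has the investigator record "the assessed relationship of the event to the study device on the Adverse Event Case Report Form", and the opening of Section 10 asks for the same single relationship. Neither mentions the procedure, the anaesthetics or the dyes.

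On anticipated risks, Section 11.4 says "All anticipated study risks are listed in Section 10.2". The only reaction to a named agent in that list is "Allergic or inflammatory reaction to medical adhesive on the iLid device".

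**The concern.** The study asks about a procedure and counts events for a device, and the two are not the same. Section 4.2 lists the System as the iLid devices, the SmartHub kit and the Express Forceps. The anaesthetics are not in that list; Section 9.3 itemises them separately as site materials. They are nonetheless a routine step of the procedure.

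The plan is purely descriptive (Section 12.7), has no hypothesis (12.1) and no pass/fail criteria (12.3). In such a study the label on the adverse-event table is in effect the safety conclusion. If the table counts device-related events only, it can be correct as labelled and still not fully answer the question in Section 2.

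A second, separate matter is the risk list. It is presented as complete, but it does not name as a cause of reaction the anaesthetics or dyes that the protocol has sites instil.

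**Working it through.** No arithmetic applies. The plan gives no calculated sample size, no adverse-event rate and no safety threshold, so there is no figure to reproduce. The check is a comparison of sections.

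1. **What is being evaluated.** Section 2 and the synopsis: the procedure.
2. **What the procedure contains.** Section 9.5.3: heat (steps 1 to 8), two topical anaesthetics (step 9), forceps expression (step 10). Every subject whose procedure reaches step 9, of up to 30, receives both.
3. **What the device contains.** Section 4.2: iLid devices, SmartHub kit and forceps. Harm from heat, adhesive or expression can therefore be rated device-related. Of the treatment steps, the anaesthetics are what lies inside the procedure but outside the device.
4. **What is captured.** Section 10.1 defines an adverse event without requiring a causal link, in a subject who has been treated with the device. Step 9 follows heating, so a reaction to the anaesthetic meets that definition. The opening of Section 10 requires ocular events to be documented whatever their cause. An ocular anaesthetic reaction is therefore recorded.
5. **What is attributed.** Sections 10 and 10.3 ask for relationship to the study device only. The adverse device effect definition in 10.1 also refers to the device, at the level of possible relationship.
6. **What enters the endpoint.** Section 6.2: device-related events. A reaction from item 4 that is judged unrelated to the device under item 5 does not enter. With no procedure field, it also cannot be told apart later from a coincidental event in any systematic way.
7. **Whether all events are captured.** The parenthetical remark in 6.2 covers all adverse events. The opening of Section 10 requires documentation of those occurring in the eye. Section 10.3 separately covers non-ocular serious events. For a non-ocular, non-serious event the two statements differ.
8. **Whether the risk list matches the agents used.** Section 10.2 says that it draws on study testing methods among other sources. Table 2 schedules tear breakup time and both staining exams at all three visits, with fluorescein (20.4) and lissamine green (20.6). Section 9.5.3 adds the anaesthetics. The list names none of these agents. The Section 10.1 definition of an unanticipated adverse device effect depends on whether a serious effect was previously identified in the plan, so the content of the list has some operational weight.

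**The case against.** The strongest reply is that little is lost. Ocular events are documented whatever their cause, visual acuity is a safety endpoint that needs no attribution, and heat and forceps harm both fall within the device. The threshold for an adverse device effect is only possible relationship, and expression is to begin within 3 minutes of heating, so an ocular surface event after that sequence may well be rated device-related. Sections 3, 7 and 12.2 also speak of the safety of the System, which a device-related endpoint fits. Finally, no decision rule depends on the count.

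Most of this stands, and it limits the point to the ancillary agents. It does not remove it. The synopsis and Section 2 name the procedure, and 9.5.3 places the anaesthetics inside it. Whether a reaction passes the threshold of possible relationship is left to judgement at 2-3 sites without a rule. Recording an event is also not the same as reporting it: Section 12.7 does not commit to tabulating events regardless of attribution.

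Several stronger readings are tempting, and the documents do not support them:

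- **That the endpoint understates procedure harm, or will read zero.** This would require that such reactions occur and that each one is confidently attributed to the anaesthetic alone. The documents show neither.
- **That omissions from 10.2 lower the event count.** They do not; an unlisted event is still an adverse event. The omission bears on risk disclosure and on what counts as unanticipated.
- **That dye reactions are missed procedure harm.** The dyes belong to the assessments in Appendix A, not to the procedure. A dye reaction at Baseline before treatment would not meet the Section 10.1 definition of an adverse event.
- **That Section 11.4 is plainly false.** The list gives mostly manifestations, such as conjunctival injection, eyelid swelling and ocular surface discomfort, which could describe an agent reaction. What can be said is that the adhesive is the only agent named.

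**Conclusion.** The point holds in limited form. The adverse-event endpoint and its attribution are narrower than the stated objective, and the difference is the anaesthetic step of the procedure. A reaction to those agents judged unrelated to the device would be recorded if ocular, but could be absent from the headline safety measure.

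The size cannot be derived. The documents give no rate of anaesthetic reactions and no rule for attributing them, so any percentage would be an invention. What is known is the exposure: every subject, of up to 30, whose procedure reaches step 9.

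The conclusion rests on two assumptions. One is that the adverse-event form, which is not in the documents, carries only the relationship item that Sections 10 and 10.3 describe. The other is that an investigator could reasonably judge an anaesthetic reaction unrelated to the device. The mismatch over which events are captured (6.2 against Section 10) and the gap between 10.2, 11.4 and the agents in use are matters of text and depend on neither.

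**What to change.** 1. In the synopsis and Section 6.2, define the endpoint as device- or procedure-related adverse events, with device-related events shown as a subset.
2. Add one relationship-to-procedure item to the adverse-event form, worded to include the ancillary agents given in 9.5.3, and amend Sections 10 and 10.3 to match. A finer split by component is not needed: with up to 30 subjects and steps minutes apart, separating anaesthetic from forceps would often be guesswork.
3. State in Section 12.7 that all recorded adverse events will be tabulated regardless of attribution, in the safety-evaluable subjects of Section 12.4.
4. Reconcile Section 6.2 (all adverse events) with the opening of Section 10 (events in the eye), so that sites know whether to record non-ocular, non-serious events.
5. Reconcile Sections 10.2 and 11.4 with the anaesthetics in 9.5.3 and the dyes in Appendix A, and carry any change into the consent template.

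The cost is edits to the protocol text and one added form field, with no extra visits, staff or subjects. The downside is that the headline event rate may be slightly higher; showing the device-related subset keeps the device-only figure available.

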7 STUDY DESIGN

This is a prospective, single-arm, exploratory treatment study. This is a post-market study intended to collect clinical data regarding the safety and effectiveness of the TearCare System. To reduce potential bias in the study, study staff performing the endpoint assessments will be independent of the clinician performing the TearCare procedure.

In this study, all subjects will receive the TearCare procedure. The TearCare procedure includes an in-office 15 minute treatment session with the TearCare System immediately (i.e. within 3 minutes) followed by manual expression of the meibomian glands using the Express Forceps. Subjects will receive one in-office TearCare procedure at the baseline visit and will then have follow-up visits at 1 week and 1 month.

This study will be conducted at 2-3 sites in the United States.

8 STUDY SELECTION CRITERIA

8.1 INCLUSION CRITERIA

For inclusion in this study, subjects must meet all of the following criteria:

1. At least 22 years of age
2. Reports dry eye symptoms within the past 3 months
3. Reports having to use artificial tears or lubricants regularly over the past month to relieve dry eye symptoms.
4. OSDI Score of ≥ 23
5. TBUT of ≤ 7 seconds in both eyes
6. Meibomian gland obstruction in both eyes based on a total Meibomian Gland Secretion Score ≤ 15 in each eye.

7. At least 15 glands in each lower eyelid should be expressible, with a sterile cotton swab, at the slit lamp.
8. Best spectacle corrected visual acuity of 20/100 or better in both eyes.
9. Willing and able to comply with the study procedures and follow-up
10. Willing and able to provide informed consent
11. English-speaking

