8.2 EXCLUSION CRITERIA

A subject who meets any of the criteria listed below (in either eye) will be excluded from the study:

1. Any active, clinically significant ocular or peri-ocular infection or inflammation
2. Recurrent clinically significant eye inflammation, other than dry eye, within 3 months prior to enrollment
3. History of eyelid, conjunctiva or corneal surgery (including refractive surgery) within the past year. In addition, subjects with any history of the following are excluded: chalazion surgery, surgery on the tarsal conjunctiva, radial keratotomy (RK), complicated blepharoplasty, lid reconstruction, or significant complications post-refractive surgery.
4. Any office-based dry eye treatment (e.g. IPL, thermal pulsation [Lipiflow], etc.) within 12 months prior to enrollment. In addition Blephex or debridement within 3 months prior to enrollment is an exclusion.
5. Meibomian gland expression within 6 months prior to enrollment. In addition, any history of meibomian gland probing is an exclusion.
6. In the clinical judgement of the investigator, meibomian glands have significant capping, atrophy, or are unable to be expressed, digitally or with a sterile cotton swab.
7. Contact lens use within the past 2 weeks (Subjects must refrain from wearing contact lenses for the duration of the study.)
8. Use of TrueTear device within the past 2 weeks (Subjects must refrain from using the TrueTear device for the duration of the study.)
9. History of Ocular Herpes Simplex or Ocular Herpes Zoster
10. Clinically significant ocular surface abnormalities that may affect tear film distribution or treatment (e.g. pterygium, anterior membrane dystrophy, etc.)
11. Clinically significant eyelid abnormalities in either eye (e.g. entropion/ectropion, blepharospasm, aponeurotic ptosis, lagophthalmos, notching of lid margin, distichiasis, trichiasis)
12. Clinically significant anterior blepharitis. In addition, collarettes or flakes of more than one quarter of the eyelid are excluded.
13. Clinically significant dermatologic or cutaneous disease of the eyelid or periocular area

14. Ocular trauma within 3 months prior to enrollment
15. Any active, clinically significant allergic, vernal, or giant papillary conjunctivitis
16. Known history of diminished or abnormal facial, periocular, ocular or corneal sensation

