9.5.2 BASELINE EXAMS AND QUESTIONNAIRES

After the subject has signed the informed consent form and agreed to participate in the study, the exams, tests and questionnaires listed in the Baseline column of Table 2 should be performed. Refer to Appendix A for instructions for performing the exams and administering the questionnaire.

At this visit, subjects should undergo the following tests and exams, performed in the order indicated below, to screen them for the study qualification and to record baseline data. Endpoint assessments (indicated with a *) should be performed by independent study staff who does not perform the TearCare procedure on study subjects.

1. OSDI Questionnaire
2. Demographics, medical and ocular history
3. Medication use: ocular and systemic
4. Best-spectacle corrected visual acuity*
5. Slit Lamp Exam*
6. Tear Breakup Time*
7. Corneal staining*
8. Conjunctival staining*
9. Meibomian Gland Secretion Scoring*

If, at any point during the visit the subjects fails to meet a subject selection criterion, then the visit can be terminated. Subjects who fail to meet all the selection criteria will be considered a screen failure and will be withdrawn from the study. Screen failures will not count toward the total enrolled and treated number of subjects.

NOTE: Questionnaire and exam data collected on subjects prior to enrollment as part of the routine clinical practice may be used to pre-screen patients for the study. However, once the subject signs the consent form and is enrolled in the study, these questionnaires and exams must be repeated following the protocol procedures.

After all required measurements have been obtained and it has been confirmed that the subject meets all the Subject Selection Criteria, then the subject will receive the TearCare procedure.

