9.6 FOLLOW-UP VISITS

Prior to the Visit: Reminder Call

Since dry eye drops and lubricants can affect the endpoint assessments, it is important to call subjects a few days before their follow-up visits to remind them that on the day of the Follow-up visit, they should not to use any of these products before the Follow-up visit.

Order of Procedures During the Follow-Up Visit

Follow-up exams should not be performed by the clinician who performed the TearCare procedure.

Follow-up procedures will be performed per the Study Schedule provided in Table 2 (page 25) and the methods included in Appendix A. Since certain tests/exams can impact the ability to perform other tests/exams, the following tests and exams should be performed in this order:

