20.3 SLIT LAMP EXAM

A standard slit-lamp examination shall be performed including inspection of the cornea at a magnification of 10X and 16X for the presence or active inflammation or structural

change, the iris and anterior chamber for inflammation, and the eyelids for crusts, collarettes, or scales.

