20.5 CORNEAL STAINING

[figure not shown]
Corneal staining should be assessed immediately following TBUT measurements (i.e. within 1-4 minutes after instillation of fluorescein dye) to assure the dye does not diffuse into stroma, blurring the discrete margin of any staining defects. A yellow Wratten filter should be used to improve any visualization of corneal staining. Grade the corneal staining using the NEI/Industry Grading System provided in Figure 4 below.²⁸

Figure 4: NEI/Industry Grading System for Corneal and Conjunctival Staining

Score each of 5 areas of the cornea and total score:

Score each of 6 areas of the conjunctiva and total score:

Add cornea and conjunctival scores for total score

[figure not shown]

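### Does the unlisted swab check of gland expressibility undermine the baseline measurements?

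*Combined protocol and SAP*

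**What the plan says.** Section 8.1, inclusion 7, sets the requirement: "At least 15 glands in each lower eyelid should be expressible, with a sterile cotton swab, at the slit lamp". Section 8.2, exclusion 6, removes subjects in whom, in the investigator's judgement, "meibomian glands have significant capping, atrophy, or are unable to be expressed, digitally or with a sterile cotton swab".

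Section 9.5.2 governs the Baseline visit. It states "At this visit, subjects should undergo the following tests and exams, performed in the order indicated below" and lists nine steps: OSDI, history, medications, visual acuity, slit lamp exam, TBUT, corneal staining, conjunctival staining and Meibomian Gland Secretion Scoring (MGSS). The visit may stop as soon as a criterion fails. Routine pre-consent data may be used to pre-screen, but after consent "these questionnaires and exams must be repeated following the protocol procedures". Finally, once every required measurement is in hand and "it has been confirmed that the subject meets all the Subject Selection Criteria, then the subject will receive the TearCare procedure".

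Section 9.6 fixes an order for the follow-up visits and gives a reason: "Since certain tests/exams can impact the ability to perform other tests/exams". In Appendix A, section 20.3 says "A standard slit-lamp examination shall be performed including inspection of the cornea at a magnification of 10X and 16X" and goes on to the iris, anterior chamber and lid debris, without gland expression. Section 20.5 says "Corneal staining should be assessed immediately following TBUT measurements". Section 20.7 scores secretions with the Meibomian Gland Evaluator, not a swab.

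**The concern.** The protocol orders its Baseline exams carefully, yet leaves out one manoeuvre that presses on the lower lids. If that pressing changes the tear film or empties glands, its place in the visit matters. Because the check is not among the follow-up steps either, any disturbance would fall on Baseline alone.

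Section 6.1 defines the effectiveness endpoints as mean changes from baseline, and section 7 provides no control arm. A baseline shift would therefore be read as part of the treatment change. It could also affect who qualifies, since the TBUT limit (7 s or less) and the MGSS limit (15 or less) use the same baseline measurements. With two or three sites and no instruction, practice might differ between them.

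**Working it through.** **1. Is the check really unlisted?** Going through the lists, it appears in 0 of 9 ordered Baseline steps (9.5.2), 0 of 13 rows of Table 2, 0 of 8 ordered follow-up steps (9.6) and 0 of 7 Appendix A methods (20.1 to 20.7). These counts describe one omission, not four.

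**2. Can MGSS stand in for it?** No. The instrument differs. Also, section 20.7 grades 15 glands per eye from 0 (nothing) to 3. If all 15 had to yield something, the total would be at least 15 x 1 = 15. Inclusion 6 requires 15 or less, so only a score of exactly 15 could qualify. The swab check is a separate act.

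**3. Where does the text put it?** Section 9.5.2 has three stages: listed measurements in a fixed order, confirmation of all criteria, then treatment. A manoeuvre outside the list fits the second stage. Placing it between two listed steps would interrupt an order the section asks sites to keep. An early check is not forbidden, because the visit may end at any point, but it is the less natural reading.

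**4. Which endpoints would be exposed at each position?**

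| Position of the check | Sign endpoints measured afterwards |
|---|---|
| With step 5 (slit lamp) | 4: TBUT, corneal staining, conjunctival staining, MGSS |
| Between steps 7 and 8 | 2: conjunctival staining, MGSS |
| Between steps 8 and 9 | 1: MGSS |
| After step 9 | 0 |

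The gap between steps 6 and 7 is closed by section 20.5. OSDI is step 1 and is not exposed.

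**5. What would a shift do?** For one endpoint, let B be the undisturbed baseline, F the follow-up value and d the shift caused by the check. The recorded change is F - (B + d) = (F - B) - d. If a fraction f of subjects is checked first, the pooled mean change moves by -f x d:

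- every site checks first: f = 1, shift -d;
- one of two equally enrolling sites: f = 1/2, shift -d/2;
- one of three equally enrolling sites: f = 1/3, shift -d/3.

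The documents give neither the size nor the sign of d. A positive d for TBUT or MGSS would understate the improvement; a negative d would overstate it.

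**6. Scale.** The only yardstick is the pilot in section 5.2, which used 12 minutes of heat and different entry criteria. Its four-week changes were 14.8 - 3.1 = 11.7 s for TBUT and 41.0 - 6.3 = 34.7 points for the gland score. As an illustration, take a tenth of the TBUT change, 1.17 s, as the smallest distortion worth noticing (my assumption). The check would then have to move baseline TBUT by 1.17 s with f = 1, by 2 x 1.17 = 2.34 s with f = 1/2, or by 3 x 1.17 = 3.51 s with f = 1/3. Nothing in the documents suggests a shift of that size, although nothing rules it out.

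**The case for a change.** The strongest case for a change is that the obvious escapes are closed. The check cannot be folded into MGSS (step 2 of the working). It is not described within the slit lamp exam, and if the words about the slit lamp were taken to place it there, it would fall immediately before TBUT. It cannot simply be settled at pre-screening, because exams are to be repeated after consent. Permission to end the visit once a criterion fails also gives a busy site a practical reason to check early. A line fixing the position would cost almost nothing.

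The omission, and the incentive to check early, both stand. The step from there to bias does not. Section 9.6 speaks of the ability to carry out other exams, and does so for follow-up visits; it does not say that a swab check alters TBUT, staining or gland scores. Exclusion 5 bars gland expression in the preceding six months, but gives no reason and does not say whether a diagnostic swab test counts.

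Nor is a fixed late position free of carry-over. After MGSS, the swab count would follow 10 to 15 seconds of evaluator pressure on each of three thirds, that is 3 x 10 = 30 to 3 x 15 = 45 seconds on each lower lid. That could influence criterion 7, and so who is enrolled.

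**Conclusion.** The check is required and unlisted, but no change to the plan follows. Read as written, section 9.5.2 leads a site to complete steps 1 to 9, confirm the criteria and then treat, which exposes 0 endpoints. The adverse reading, with the check beside step 5, exposes 4, by an amount and in a direction that the documents do not establish.

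The consequences are limited as well. Sections 12.1, 12.3 and 12.7 set no hypothesis, no pass/fail criterion and only descriptive statistics, so no test or decision rule can be distorted. Section 13 has staff trained in subject selection at site initiation, a natural place to settle when and by whom the check is done.

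This conclusion rests on two assumptions: that sites keep to the listed order, and that any shift from a swab check is small beside the changes under study. The pilot gives only indirect support for the second. Evidence that sites checked before TBUT and that the swab materially moved the readings would reopen the point.
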